6.3. Recruitment

Participants of the already recruited ABC-PD cross-sectional cohort (ethic protocol 686/2013B01) will be asked to participate in the follow-up assessment. Patients who did not agree to participate in a longitudinal study or who have asked not to be contacted after the first cross-sectional assessment will not be contacted again. A drop-out rate of 20% is expected for follow-up retention. Therefore, investigation of 209 patients will be conducted between August 2018 and April 2020. During the executive project phase, three patients will be assessed weekly (~12 per month). Patients will be contacted either via phone or in written form. Reason for drop-outs will be registered for data analysis.

7. Statistics and Sample size estimation

The relative risk as well as the positive and negative Likelihood Ratios according to baseline group status for conversion to PD-MCI or PDD will be calculated.

1. Between-group differences will be conducted using either a Student's t-test, analyses of variance (ANOVA), or covariance analyses.
2. For longitudinal within-group analyses of cognitive and ADL progression, we will use either paired t-tests or repeated ANOVA models. Additionally, Kaplan Mayer survival curves and Cox proportional hazard models stratified by the individual group status (e.g. PD-MCI with and without cognitive-driven ADL impairment) will be applied to estimate the time period to PD-MCI or PDD conversion.
3. Associations between serum and CSF markers along with ADL and cognitive data will be carried out using multivariate regression analyses in order to evaluate the type of biomarker that best reflects the biological impact on phenotype and progression.

Reports on conversion rates of new-onset PD-MCI and PDD are highly variable between studies [5]. At a mean follow-up interval of around four years, the frequency of PDD in large

PD cohorts is estimated to vary between 13% [7] and 28% [27], resulting in 27 to 58 patients with PDD in the present cohort at follow-up. New-onset PD-MCI is expected to be higher, with around 49 (36%) [6] to 107 (78%) cases in our cohort [27]. Of all PD-MCI patients, one-third are classified as having cognitive-driven compared to motor-driven ADL impairment, resulting in at least 16 to 35 new-onset PD-MCI patients classified as FAQ_{Q>1} [24]. These estimates resemble the sample size of our preliminary data described above, for which between-group differences have been statistically verified. Therefore, we conclude that moderate to strong effects can be detected with 80% power in two-group comparisons.

8. Assessments

Table 1: Overview of assessments

Assessment of PD patients	Time
Explanation of the study requirements	10 min
Demographics & lifestyle	
Age, gender, education, occupation, family history of neurodegenerative diseases, smoking/drinking behavior, height & weight	5 min
Neurological Assessments:	
Medication intake, concomitant diseases, and procedures	10 min
Unified Parkinson's Disease Rating Scale (UPDRS) Parts III-IV, Hoehn & Yahr Stage	15 min
Olfactory testing using the Sniffin Sticks 12 odor test	3 min
PD Non-Motor Symptom Scale, subscales 1-5 (PD-NMS-S)	5 min
Unified Multiple System Atrophy Rating Scale (UMSARS) I: History of autonomic symptoms	2 min
Cognitive test battery:	
History and self-awareness of cognitive deficits	5 min
Montreal Cognition Assessment (MoCA)	10 min
Mini Mental State Examination (MMSE)	5 min
Consortium to Establish a Registry for Alzheimer's Disease (CERAD-Plus, German Version)	25 min
Trail Making Test Parts A and B	10 min
Fragmented Words (Subtest of the Leistungsprüfssystem für 50- bis 90-Jährige, LPS 50+)	5 min
Digit-Symbol Test (Subtest of the Wechsler Intelligenztest für Erwachsene, WIE)	5 min
Similarities (Subtest of the WIE)	5 min
Letter-Number Sequencing (Subtest of the WIE)	5 min
Demenz Apraxie Test (DAT)	5 min
Pill-Questionnaire	5 min
Patient Questionnaires (can be filled out at home):	
Parkinson's Disease-Non-motor Symptoms Questionnaire (PD-NMS-Q)	3 min
Beck Depression Inventory – II (BDI-II)	5 min
Geriatric Depression Scale (GDS)	2 min
Beck-Anxiety-Inventory (BAI)	2 min
Functional Activities Questionnaire (FAQ)	2 min
Parkinson's Disease Activities of Daily Living Scale	1 min
Parkinson's disease Questionnaire (PDQ-39)	5 min
Freezing of Gait Questionnaire (FOG)	1 min
Epworth Sleepiness Scale (ESS)	2 min
REM Sleep behavior questionnaire (RBDS-Q)	2 min
Apathy Evaluation Scale (AES)	3 min
Questionnaire for Impulsive-Compulsive Disorders in Parkinson's Disease-Short (QUIP-Kurz)	3 min
Unified Parkinson's Disease Rating Scale (UPDRS) Parts I-II	6 min
International Consultation on Incontinence Questionnaire-Short Form (ICIQ-SF)	2 min
Patient Perception of Bladder Condition (PPBC)	1 min
Top-10 Priority List	5 min
Saarbrücker Persönlichkeitsfragebogen (SPF)/ Interpersonal Reactivity Index (IRI)	5 min
Total time of clinical assessment:	185 min
Optional Home-based movement assessment (Accelerometer)	7 days

For this scientific study, all investigations will be performed in an ambulatory setting and need the study participants to be available for at least 3 hours and 5 minutes, not including the optional blood marker sampling (blood: 15 min, CSF: 30 min). To evaluate the association between the onset and severity of both motor and non-motor symptoms which might indicate disease progression and are therefore more pronounced in PD patients with mild ADL dysfunction, a comprehensive clinical assessment will be conducted.

- If patients agree to the optional CSF and/or blood collection (see also 8.6):
 - Blood collection 15 min
 - CSF 30 min**Total time for biomarker sampling:** 45 min

Caregiver assessments:

To validate the patient's self-impression, the following caregiver questionnaires and interview scales will be applied, needing caregivers to be available for at least 40 minutes. Caregiver assessments will only be performed if the respective patient has agreed to the interview.

Table 2: Overview of caregiver assessments

Assessment	Time
Explanation of the study requirements	10 min
Interview-based ratings:	
Informant Questionnaire on Cognitive Decline in the Elderly (IQ-CODE)	6 min
Tübinger Activity of Daily Living Inventory for Parkinson's disease	6 min
Questionnaires:	
Pfeffer Functional Activities Questionnaire (FAQ)	4 min
Bayer Activities of Daily Living Scale (Bayer ADL)	5 min
Top-10 Priority List	5 min
Saarbrücker Persönlichkeitsfragebogen (SPF)/ Interpersonal Reactivity Index (IRI)	4 min
Total Time of caregiver assessment:	40 min

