3.2. Preliminary data

Methods. In a cohort of 216 non-demented PD patients (41.2%, with PD-MCI), assessed within the frame of the ongoing "Amyloid-Beta in Cerebrospinal Fluid as a Risk Factor for Cognitive Dysfunction in Parkinson's Disease" (ABC-PD) study, we developed a novel quotient score from the Pfeffer Functional Activities Questionnaire (FAQ) [24]. The FAQ is a 10 item instrumental ADL assessment scored on a 4-point Likert scale ranging from normal (score=0) to dependent (score=3) ADL function (max. points 30) [25].

The novel FAQ quotient was developed by differentiating cognitive and motor aspects of the individual items. Ten linear regressions were conducted defining each FAQ item as the dependent variable, and the Unified Parkinson's Disease Rating Scale-Part III (UPDRS-III), motor assessment) as well as the Montreal Cognitive Assessment (MoCA) total score as independent variables, with age, sex, and disease duration entered as covariates.

Results Part 1: Construction of FAQ-Quotient. As a result, the items 1-(accounting for finances), 2-(tax/business records) and 9-(remembering important events) showed associations with the MoCA score, whereas the items 3-(shopping alone), 4-(skills & hobbies), 5-(using appliances), 6-(meal preparation), 10-(traveling out of house) were found to be significantly associated only with the UPDRS-III score. Item 7-(current events) and 8-(information intake) were associated with both motor and cognitive function and were therefore included into both scores as a constant. Based on the regression analyses, the set of items for cognitive function was defined as, $S_{cog} = \{1,2,7,8,9\}$ while the set of items reflecting motor function was defined as $S_{mot} = \{3,4,5,6,7,8,10\}$. If S_i denotes the score obtained in item i for a patient and $S_{i,max}$ denotes the maximum score possible for item i , then the following subscores were defined as:

$$FAQ_C = \sum_{i \in S_{cog}} \frac{S_i}{S_{i,max}} \quad FAQ_M = \sum_{i \in S_{mot}} \frac{S_i}{S_{i,max}} \quad FAQ_Q = \frac{FAQ_C + 1}{FAQ_M + 1}$$

FAQ_Q: The quotient was formed by dividing the cognitive aspect (FAQ_C) by the motoric aspect (FAQ_M); a value >1 (FAQ_{Q>1}) indicates more cognitive- compared to motor-related ADL impairment.

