Results Part 2: Validation of FAQ-Quotient. Out of the 89 PD-MCI patients, 32.6% presented with FAQ_Q values >1 , while 67.4% had an FAQ_Q ≤ 1 . The frequency of males was comparable between both PD-MCI subgroups (FAQ_{Q>1} 65.5%, FAQ_{Q≤1} 63.3%; $p=0.99$). Logistic regression analyses showed that patients defined as PD-MCI FAQ_{Q>1} were more impaired in tests assessing attention/working memory ($p=0.033$) and language performance ($p = 0.019$) than the PD-MCI FAQ_{Q≤1} group, while motor symptom severity revealed no significant difference between groups ($p=0.095$). Therefore, subgrouping PD-MCI patients according to the cognitive and motor performance in the FAQ is suitable for differentiating between different levels of severity for cognitive impairment in PD.

4. Objectives of the study

The FAQ is an economic and easy to apply ADL scale. Items of the FAQ have been previously published [25, 26]; details of the construction of our FAQ parameters are currently under review for publication and will also be available without additional costs.

The aim of our project is to evaluate whether the combination of PD-MCI along with cognitive-driven ADL impairment predicts the future development of PDD and might be able to differentiate between those PD-MCI patients with a high risk for the development of PDD from those with stable PD-MCI. The identification of a high-risk group for PDD among those with PD-MCI is essential for upcoming clinical trials targeting cognitive impairment in its earliest stages.

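### Section 7 compares groups expected at about 1:2 with the pooled-variance Student's t-test, which misses its nominal level in either direction if spreads differ; FAQ_Q, if analysed as a continuous score, belongs on the log scale

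*Combined protocol and SAP*

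**What the plan says.** Section 7 of the combined protocol and SAP lists the tests. Item 1, for between-group differences, offers Student's "t-test, analyses of variance (ANOVA), or covariance analyses". Item 2, for within-group change in cognition and ADL, says "we will use either paired t-tests or repeated ANOVA models". Neither item mentions unequal variances, a transformation, or which ADL score is meant.

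Section 3.2 defines the measure that forms the groups: "The quotient was formed by dividing the cognitive aspect (FAQ_C) by the motoric aspect (FAQ_M"), with 1 added to each part. It reads the result against 1: "a value >1 (FAQ_{Q>1}) indicates more cognitive- compared to motor-related ADL impairment". On the resulting split it reports: "Out of the 89 PD-MCI patients, 32.6% presented with FAQ_Q values" above 1, and 67.4% at or below 1. The sample size text in Section 7 carries the one-third share forward and expects 16 to 35 new-onset PD-MCI patients above 1.

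The hypothesis and Aims 2.1 and 3.1 in Section 4.1 use FAQ_Q as a two-level status, above 1 or not.

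**The concern.** With equal group sizes, Student's t-test tolerates unequal variances fairly well. At 1:2 it does not, because the pooled variance is weighted towards the larger group while the uncertainty of the difference comes mostly from the smaller one. If the smaller group varies more, the standard error is too small and there are too many false positives. If it varies less, the test is conservative and power is lost. ANOVA and covariance analysis rest on the same assumption; with two groups, one-way ANOVA is the same test. This affects any comparison of cognition, motor score, biomarkers or change between the FAQ_Q groups.

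The second issue is scale. A paired t-test needs a quantitative ADL score, and FAQ_Q is the ADL measure at the centre of the study. It is a ratio with a neutral value of 1, so its raw mean depends on its spread as well as on its centre.

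**Working it through.** **1. Group sizes.** From Section 3.2: 89 × 0.326 = 29 and 89 × 0.674 = 60. From Section 7: 49/3 and 107/3 give the stated 16 and 35, leaving 49 − 16 = 33 and 107 − 35 = 72 in the other group. All are close to 1:2. The plan states 80% power but no alpha, effect size or SD, so that figure cannot be reproduced. A two-sided 5% level is assumed below.

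**2. Why the pooled test drifts.** Let the larger group (n = 60) have SD 1 and the smaller (n = 29) have SD k.

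- Variance the test uses, on average: [(28k² + 59)/87] × (1/29 + 1/60), where 1/29 + 1/60 = 0.05115.
- True variance of the difference: k²/29 + 1/60.
- With R the square root of used over true, the rejection rate under equal means is roughly 2 × [1 − Φ(1.988 × R)].

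For k = 2: used = (171/87) × 0.05115 = 0.1005; true = 0.1546; R = 0.806; rate about 10.9%.

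For k = 0.5: used = (66/87) × 0.05115 = 0.0388; true = 0.0253; R = 1.239; rate about 1.4%.

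**3. Simulation.** Normal data, equal means, 29 vs 60, 40,000 runs per row, nominal 5%:

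| SD ratio, smaller/larger group (assumed) | Student | Welch |
|---|---|---|
| 0.5 | 1.7% | 5.0% |
| 0.67 | 2.5% | 4.8% |
| 1 | 4.8% | 5.0% |
| 1.25 | 6.8% | 4.8% |
| 1.5 | 8.7% | 5.1% |
| 2 | 11.4% | 4.9% |
| 3 | 14.5% | 4.9% |

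Results at 16 vs 33 and 35 vs 72 are nearly the same.

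**4. Price of Welch if variances are equal.** The standardised difference with 80% power by the normal approximation is (1.960 + 0.842) × √(1/n₁ + 1/n₂), which is 0.63 at 29 vs 60 and 0.85 at 16 vs 33. Simulated power, Student against Welch, is 79.3% against 78.7% at 29 vs 60, and 78.3% against 77.2% at 16 vs 33. The loss is 0.6 and 1.1 points.

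**5. Range of FAQ_Q.** Three items (1, 2, 9) count only in the cognitive part, five (3, 4, 5, 6, 10) only in the motor part, and two (7, 8) in both, each scaled 0 to 1. The maximum is (3 + 1)/(0 + 1) = 4 and the minimum (0 + 1)/(5 + 1) = 1/6. Full enumeration of item scores confirms both.

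**6. Raw against log scale within a group.** Suppose log(FAQ_Q) is normal with mean 0 at both visits. The raw mean is exp(s²/2): 1.05 for a log-SD of 0.3 and 1.13 for 0.5. If the log-SD grows from 0.3 to 0.5 with no shift in log-mean (assumed; correlation between visits 0.5), the raw paired t-test rejects in the cognitive direction in 9% of trials at n = 29, 20% at n = 60 and 67% at n = 209, the planned follow-up number. On the log scale it rejects in about 5% at each size. With equal spread at both visits the raw test also holds about 5%.

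**The case against.** The strongest reply is that nothing in the documents says continuous FAQ_Q enters any of these tests. The hypothesis and Aims 2.1 and 3.1 use it dichotomised, and other ADL scales are collected (the Parkinson's ADL scale, the Bayer ADL scale and the Tübingen inventory). The conversion question is answered by relative risks, likelihood ratios, Kaplan-Meier curves and Cox models, none of which depends on the scale of FAQ_Q once it is cut at 1. This stands. It makes the log-scale point conditional, but it does not touch the choice of between-group test, which applies to whatever outcome is compared.

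Three stronger readings are tempting and are not supported.

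- A reader might infer an SD ratio of 3.6 from the room above and below 1 (3.0/0.83). That is a ratio of theoretical ranges. It says nothing about the SD of cognition, motor score or biomarkers. For baseline FAQ_Q itself, equal means are impossible between groups cut at FAQ_Q = 1, so no false-positive rate exists to inflate.
- A reader might infer that false positives are certain to be inflated. The documents give no SDs, and if the smaller group has the smaller spread the test is conservative.
- A reader might infer that the raw mean must lean to cognitive-driven. It exceeds the geometric mean whenever values vary, but it need not exceed 1: assumed item-level models gave means of 0.84 to 0.93 in one set and 1.03 to 1.14 in another. No test of the mean against 1 is planned.

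It is also fair that the item 2 tests pool no variance across the FAQ_Q groups, so the 1:2 argument belongs to item 1 alone.

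**Conclusion.** The point holds in a limited form. With about 1:2 groups, the between-group test named in Section 7 keeps its level only if the variances are equal, which the plan neither shows nor assumes openly. At 29 vs 60 the actual level is about 1.7% to 2.5% for SD ratios of 0.5 to 0.67, and 8.7% to 14.5% for ratios of 1.5 to 3. These figures rest on normal data, a two-sided 5% level and assumed ratios; which side applies is unknown. Welch is near 5% in every case.

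The log-scale point applies only where FAQ_Q is used as a continuous progression score, and the false signal in step 6 arises only if its spread changes between visits. The log scale does not cure regression to the mean in groups selected at the cut-off: in simulations with no true change, the paired test in the group above 1 rejected in 30% to 59% of trials on the raw scale and 48% to 68% on the log scale.

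**What to change.** In Section 7 item 1, replace Student's t-test by Welch's t-test, and use heteroscedasticity-robust standard errors in ANOVA and covariance analyses that compare the FAQ_Q groups.

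In item 2, name the ADL score and its scale. Wherever FAQ_Q itself is analysed as a continuous score of progression, use log(FAQ_Q) and report a geometric mean ratio. State that the classification above 1 or not is kept for the hypothesis and Aims 2.1 and 3.1.

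The change is to wording only and needs no new data. If variances prove equal, it costs under 1 point of power at 29 vs 60 and about 1 point at 16 vs 33.

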3.1. Background

Presence and severity of non-motor symptoms modulates the rate of Parkinson's Disease (PD) progression with a high impact on patients' quality of life [1-3]. One major clinical milestone in the course of the disease is the conversion to Parkinson's disease dementia (PDD), dramatically increasing the risk for nursing home placement and mortality [4]. One of the greatest risk factors for PDD is the development of mild cognitive impairment in PD (PD-MCI) [5]. However, only a subgroup (26% to 39.1%) of patients with PD-MCI have been reported to convert to dementia, while others present with a stable cognitive status or revert to normal cognitive function [6-8]. For an early and effective treatment, the identification of a high-risk group for PDD among those with PD-MCI is essential.

The core feature that differentiates PDD from PD-MCI is the loss of the ability to perform activities that are necessary for independent living [9, 10], emphasizing the importance of valid and reliable activities of daily living (ADL) assessments in PD [11]. To confirm the diagnosis of PDD, ADL disabilities should be primarily caused by cognitive, not motor, dysfunction [10, 12]. As PD is primarily a movement disorder, the distinction between motor and non-motor contributions to ADL in PD is an obvious challenge [13].

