6.1. Study population

Between March 30th, 2014 and December 31th, 2017, we recruited a large cohort of 262 PD patients within the frame of the “Amyloid-Beta in cerebrospinal fluid as a risk factor for cognitive dysfunction in Parkinson’s Disease” (ABC-PD, ethic protocol 686/2013B01) study. Of the total baseline sample, 43% were diagnosed with PD-MCI (63% males, mean age of 67.2 ± 7.7 years) whereas 57% had normal cognitive function (61% males, mean age of 65.4 ± 8.7 years). Mean disease duration of the total sample was 5.1 ± 3.9 years.

We propose to follow-up the already existing ABC-PD cohort described above with a longitudinal assessment including neuropsychological in-depth endophenotyping and CSF biomarker analyses. The estimated mean follow-up interval is 46.6 ± 6.6 months.

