8.1. Retrospective Data

Data collected in the clinical routine, e.g. demographics, medication intake, concomitant diseases and procedures, disease and motor severity, detailed neuropsychological assessments, and detailed non-motor symptom assessments, will be included in the data analysis. If these parameters are collected when participating in other clinical studies, these will also be included.

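### Kaplan-Meier and Cox are planned for time to conversion, but one follow-up visit and no dating rule give status at follow-up, not onset times

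*Combined protocol and SAP*

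**What the plan says.** Section 7 opens with a status-based analysis: "The relative risk as well as the positive and negative Likelihood Ratios according to baseline group status for conversion to PD-MCI or PDD". It then adds "Kaplan Mayer survival curves and Cox proportional hazard models stratified by the individual group status", which "will be applied to estimate the time period to PD-MCI or PDD conversion".

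The design behind these analyses is one baseline and one follow-up. Section 6.1 states: "The estimated mean follow-up interval is 46.6 ± 6.6 months". Section 6.3 adds that "investigation of 209 patients will be conducted between August 2018 and April 2020". Aim 2.1 compares baseline with follow-up, and section 8.2 bases both diagnoses on Level-II testing. No section gives a time origin, a rule for dating conversion, a censoring rule or an interval-censored method.

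Other information could bear on onset. For routine-care data, section 8.1 says that "detailed neuropsychological assessments, and detailed non-motor symptom assessments, will be included in the data analysis", and for other studies: "If these parameters are collected when participating in other clinical studies, these will also be included". Table 1 includes history-taking on cognitive deficits. Section 8.5 describes the IQ-CODE, which compares present abilities with those two years before. None of these is given a role in dating a Level-II diagnosis.

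**The concern.** Standard Kaplan-Meier and Cox methods treat the event date as known. Here a converter's onset lies somewhere between two assessments about four years apart, and a patient without the outcome at follow-up is only known not to have it then. These are current-status data, the extreme form of interval censoring. Records under section 8.1 may narrow the interval for some patients, but the data stay interval-censored.

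Section 3.1 adds a complication. It says that some PD-MCI patients convert "while others present with a stable cognitive status or revert to normal cognitive function". A single later visit therefore records status at that visit, not whether the patient ever converted.

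At stake is a set of survival curves and medians reported as time to conversion that would mostly describe when patients were seen. Also at stake is some of the power for comparing the two PD-MCI groups, which is the study's hypothesis (section 4.1).

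**Working it through.** **1. The plan's own counts.** 262 × 0.80 = 209.6 (stated 209). 209 × 0.13 = 27.2 and 209 × 0.28 = 58.5 (stated 27 to 58). These reproduce. The 80% power statement cannot be reproduced, because no alpha or effect size is given.

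**2. Inputs and assumptions.**
- From the documents: visit mean 46.6 and SD 6.6 months (6.1); conversion of 13% (PDD, section 7), 26% and 39.1% (PD-MCI to dementia, section 3.1, no time frame stated), and 36% and 78% (new PD-MCI, section 7).
- PD-MCI patients at follow-up: 0.43 × 209 = 90. Of these, 0.326 × 90 = 29 have cognitive-driven impairment, leaving 61.
- Assumed: conversion dated at the follow-up visit; time from baseline; constant hazard; each percentage taken as the risk by 46.6 months; normal visit times cut to 28–73 months. The 73 is March 2014 to April 2020. The 28 is a choice; lowering it to 7, the shortest interval the stated windows allow, leaves the 26% row unchanged at this rounding.

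**3. Curves.** The hazard is λ = −ln(1 − P)/46.6 and the true cumulative conversion is F(t) = 1 − exp(−λt). For P = 26%, λ = 0.3011/46.6 = 0.00646 per month, so F(54) = 1 − exp(−0.349) = 29.5%.

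If conversion is dated at the visit, everyone not yet seen is still at risk, and a patient seen at u counts as an event with probability F(u). With visit density g and share not yet seen G, the curve is 1 − exp(−∫ [g(u)/G(u)] F(u) du).

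Hand check at 46.6 months: half have been seen, so the visit hazard sums to ln 2 = 0.693. With F about 0.238 (its value near 42 months), 0.693 × 0.238 = 0.165, and 1 − exp(−0.165) = 15%, against a true 26%.

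| Conversion by 46.6 mo | Visit-dated at 36 / 46.6 / 54 mo | True | Median, visit-dated | Median, true |
|---|---|---|---|---|
| 13% | 0.5 / 8 / 24% | 10 / 13 / 15% | 62 | 232 |
| 26% | 1 / 15 / 42% | 21 / 26 / 29.5% | 56 | 107 |
| 36% | 1.5 / 20.5 / 52.5% | 29 / 36 / 40% | 53.5 | 72 |
| 39.1% | 2 / 22 / 55% | 32 / 39 / 44% | 53 | 65 |
| 78% | 3.5 / 40 / 80% | 69 / 78 / 83% | 48 | 21 |

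Of 90 patients, about 85, 45 and 12 remain at risk at the three times. With 28% conversion and only the mean visit moved to 36, 46.6 or 58 months, the visit-dated median moves to 46.5, 55.4 or 65.4. The true median stays at 98.3.

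**4. Extra tests under section 8.1.** Coverage is unknown. If half or all patients had one extra usable test at a random time, and conversion were dated at first detection, the 36-month reading at 26% would be 6% or 11%, against a true 21%.

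**5. Group comparison, equal visit timing, 29 against 61.** Group is entered as a covariate and a true hazard ratio of 3 is assumed.
- At 26% overall, reference risk is 17.5%. The other group's risk is 1 − 0.825³ = 43.8%, a risk ratio of 43.8/17.5 = 2.5. The median visit-dated Cox estimate is 2.50.
- At 39.1% overall, reference risk is 27.9%. The other group's risk is 1 − 0.721³ = 62.5%, a risk ratio of 62.5/27.9 = 2.24. The median Cox estimate is 2.23.
- With no true effect, Cox rejects in about 4–5% of simulated cohorts.
- Cox power is about 57–60% at 26% and 63–66% at 39.1%. A comparison of proportions gives about 67–77% and 83–89%. The range covers uncorrected chi-square, Fisher and continuity-corrected tests and different simulation runs.

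**6. Unequal timing (hypothetical).** The SE of the difference in mean timing is 6.6 × √(1/29 + 1/61) = 1.49 months, so a chance gap of 3 months has about 4% probability. Such a gap would turn no effect into a Cox hazard ratio of 0.66 or 1.52 at 26%. For a status-based risk ratio, F(48.1) = 26.7% and F(45.1) = 25.3%, a ratio of only about 1.06.

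**The case against.** The strongest reply is that the plan never says conversion will be dated at the visit, or that time runs from baseline. Age or time since PD onset are possible scales, and the figures above would not carry over to them. Section 8.1 records, the history of cognitive deficits and the IQ-CODE might all inform onset. This stands as a limit on the figures: they describe one scenario, chosen because the follow-up visit is the one date every assessed patient has. It does not remove the gap, because no rule turns any of these sources into the date of a Level-II diagnosis.

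A second reply also stands. The relative risk and likelihood ratios are already planned and need only status at follow-up; the survival methods are additional to them.

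A third concerns the size of the power loss. It depends on the comparator test and on an assumed hazard ratio of 3, and it requires group to be a covariate. Section 7 says the models are stratified by group; taken literally, a stratified Cox model gives no group hazard ratio at all. The direction holds, but the size at 26% is not firm.

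A reader might infer that the Cox test is invalid, that the group comparison is spurious, or that the hypothesis cannot be tested. The documents support none of these. They do not show that visit timing differs by group, and under equal timing the test keeps its error rate.

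**Conclusion.** The concern holds in limited form and should be fixed. One scheduled follow-up and no dating rule cannot supply the time to conversion that section 7 sets out to estimate.

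Conditional on visit-dating from baseline and a constant hazard, the curves understate early conversion severely. At 54 months they overstate it in every case except 78%. Their medians stay within 48 to 62 months whatever the true course.

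Under equal timing the Cox estimate is a reasonable risk ratio but understates the hazard ratio. The power loss is roughly 8 to 18 percentage points at 26% overall (59 against 67, and 57 against 75) and 17 to 25 at 39.1% (66 against 83, and 63 against 88). A timing difference between groups would add bias, but that is hypothetical. The status-based analyses in section 7 do not depend on dating.

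**What to change.** 1. Describe the outcome as PD-MCI or PDD status at follow-up, and define time as months from baseline.
2. Drop visit-dated Kaplan-Meier curves, median times and the statement that time to conversion will be estimated.
3. Base the group comparison on the planned relative risk, adjusted for months from baseline. One way is complementary log-log regression of status on group, with log(months) as a covariate, or as an offset with the constant-hazard assumption stated. Its group coefficient is a log hazard ratio, and fitted risks near 48 months give the adjusted relative risk. In simulation with a true hazard ratio of 3 it returned 2.98 to 3.16 across Weibull shapes 0.7, 1 and 2, with power of 74% (26% overall) and 88% (39.1% overall).
4. Report follow-up length by group.
5. Optionally, where section 8.1 records qualify under a rule set in advance, add an interval-censored model as a sensitivity analysis, noting that patients with complaints may be tested more often.

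The cost is analysis-plan wording only, with no new data. The downsides are the loss of a conventional survival curve, a parametric assumption, and inference limited to the group comparison and risk near 48 months. With 90 patients at 26% overall and a hazard ratio of 3, the log(months) slope is zero or negative in 26% of fits. Reference-group risk is usable at 48 months (5th to 95th percentile 10–27%, true 18%) but not at 24 months (1–47%, true 9%). The replacement cannot estimate time to conversion either.

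### The expected new-onset PD-MCI counts in Section 7 imply 137 or 138 cognitively normal patients at follow-up, a number stated nowhere; the plan's own figures give about 119, so the counts are about 13–15% too high if drop-out is equal by cognitive group

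*Combined protocol and SAP*

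**What the plan says.** Section 6.1 reports that "we recruited a large cohort of 262 PD patients", of whom 43% had PD-MCI "whereas 57% had normal cognitive function". Section 6.3 states "A drop-out rate of 20% is expected for follow-up retention", with no split by cognitive group, and continues: "Therefore, investigation of 209 patients will be conducted between August 2018 and April 2020".

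Section 7 then gives three sets of expected counts:

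- PDD at rates of 13% to 28%, "resulting in 27 to 58 patients with PDD in the present cohort at follow-up".
- New-onset PD-MCI, "with around 49 (36%) [6] to 107 (78%) cases in our cohort [27".
- One-third of PD-MCI taken as cognitive-driven, "resulting in at least 16 to 35 new-onset PD-MCI patients classified as FAQ_{Q>1".

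The paragraph says that these estimates are similar in size to the preliminary data, and ends: "we conclude that moderate to strong effects can be detected with 80% power in two-group comparisons". It gives no denominator for the 36% and 78%.

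**The concern.** A new case of PD-MCI can occur only in someone who was cognitively normal (PD-CN) at baseline, and Aim 3.2 in Section 4.1 restricts the prediction of PD-MCI to that group. The rates of 36% and 78% should therefore apply to the PD-CN patients expected at follow-up. The printed counts imply a base well above the one that Sections 6.1 and 6.3 yield, while the PDD counts in the same paragraph do follow from 209.

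These counts are part of the only basis offered for the plan's only power statement. That statement names no test, significance level or numerical effect size, so the expected group sizes are the one element a reader can check.

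**Working it through.** **Inputs.** Baseline cohort 262; PD-CN 57%, PD-MCI 43% (Section 6.1). Overall drop-out 20%; 209 at follow-up (Section 6.3). PDD rates 13% and 28%; new-onset PD-MCI 49 (36%) and 107 (78%); FAQ_Q>1 share one-third, giving 16 to 35 (Section 7). FAQ_Q>1 share in the preliminary data: 32.6% of 89 (Section 3.2).

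**1. Figures that reproduce.**
- Follow-up sample: 262 × 0.80 = 209.6, printed as 209.
- PDD: 0.13 × 209 = 27.17 and 0.28 × 209 = 58.52, printed as 27 and 58, so truncated.

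**2. Base implied by the PD-MCI counts.** 49 / 0.36 = 136.1 and 107 / 0.78 = 137.2. The only integers for which 49 is 36% and 107 is 78%, to whole percents, are 137 and 138.
- If counts are rounded, 137: 0.36 × 137 = 49.32; 0.78 × 137 = 106.86.
- If counts are truncated, 138: 0.36 × 138 = 49.68; 0.78 × 138 = 107.64.

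As a share of the follow-up sample, 137 / 209 = 65.6% and 138 / 209 = 66.0%, against the stated 57%.

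**3. Base from the plan's own figures, with equal drop-out.** 0.57 × 209 = 119.1. Allowing for rounding of the 57% (56.5% to 57.5%), the range is 118.1 to 120.2.

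**4. Other bases the documents could support.** None gives 49 and 107.

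| Base | N | 36% | 78% |
|---|---|---|---|
| 57% of 262, no drop-out | 149.3 | 53.8 | 116.5 |
| PD-CN in the preliminary cohort, 58.8% of 216 | 127 | 45.7 | 99.1 |
| 58.8% (preliminary PD-CN share) of 209 | 122.9 | 44.2 | 95.9 |
| 209 less 27 PDD | 182 | 65.5 | 142.0 |
| 209 less 58 PDD | 151 | 54.4 | 117.8 |
| All 209 | 209 | 75.2 | 163.0 |

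**5. Counts on a base of 119.** New-onset PD-MCI: 0.36 × 119 = 42.84 and 0.78 × 119 = 92.82. One-third of these: 14.28 and 30.94.

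| | Printed | Rounded | Excess | Truncated | Excess |
|---|---|---|---|---|---|
| New-onset PD-MCI, low | 49 | 43 | 14.0% | 42 | 16.7% |
| New-onset PD-MCI, high | 107 | 93 | 15.1% | 92 | 16.3% |
| FAQ_Q>1, low | 16 | 14 | 14.3% | 14 | 14.3% |
| FAQ_Q>1, high | 35 | 31 | 12.9% | 30 | 16.7% |

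**6. Effect on detectable differences.** The plan specifies no test. For scale, assume a two-sided 5% t-test of FAQ_Q>1 against FAQ_Q≤1 within new-onset PD-MCI, at 80% power. The detectable standardised difference then moves as follows:
- Low end: from 0.87 (16 vs 33) to 0.93 (14 vs 29).
- High end: from 0.58 (35 vs 72) to 0.62 (31 vs 62).

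**The case against.** **Drop-out may not be equal.** Sections 6.2.1 and 6.2.2 require that patients can understand and comply with the study and can complete the consent form. After about four years, those rules could remove more baseline PD-MCI than PD-CN patients and raise the PD-CN share above 57%. At illustrative shares of 60%, 62% and 64%, the base is 125, 130 and 134, and the excess of 137 over it falls to about 9%, 6% and 2%; at 64% the low FAQ_Q>1 count is again 16. This stands as a limit on the size of the error. It does not supply the missing base. To reach 137 of 209, retention would have to be 137 / 149.3 = 92% in PD-CN and (209 − 137) / 112.7 = 64% in PD-MCI, which the plan nowhere states.

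**The upper FAQ_Q>1 figure depends on the rounding rule.** The printed 35 comes from truncating one-third of 107 (35.67) or from rounding 32.6% of 107 (34.88). On 119, either route gives 30 (30.94 truncated; 0.326 × 93 = 30.32). A revised figure of 31 comes from rounding one-third. The point is fair, but it moves the result by one patient, and in the direction of a larger discrepancy.

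**The consequence is small.** The power sentence argues from resemblance to the preliminary data: 89 PD-MCI patients, of whom 32.6% (29) had FAQ_Q>1. Both the printed and the revised ranges contain 89 and 29. The main hypothesis also concerns patients with PD-MCI at baseline, not new-onset cases. Both points stand, and they keep this a minor correction.

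**Conclusion.** The point holds and is minor. Two parts carry different certainty. That the base for 49 (36%) and 107 (78%) is unstated, and is not 57% of 209, follows directly from the document and needs no assumption. That the counts are too high by about 13–15% (14–17% if truncated) rests on equal drop-out in PD-CN and PD-MCI; higher retention of PD-CN would shrink the gap. On equal drop-out, the low FAQ_Q>1 count is 14, so 16 cannot be presented as a minimum. The conclusion about moderate to strong effects is not overturned, because the shift is small relative to the span of the planning range.

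**What to change.** In Section 7, name the base and restate the counts, for example:

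> Among about 119 patients cognitively normal at baseline and seen at follow-up (57% of 209, assuming equal drop-out by cognitive group), about 43 (36%) to 93 (78%) are expected to develop PD-MCI, of whom about 14 to 31 would be FAQ_Q>1.

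Use one rounding rule throughout; if counts are truncated, as the PDD counts are, the figures are 42 to 92 and 14 to 30. Delete the words *at least*, and relate the 80% power statement to these sizes. If a different base was intended, state it and show its derivation, including any drop-out rates by cognitive group.

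The cost is the wording of one paragraph, and the planning figures become slightly less favourable. The cohort is already recruited, so the target of 209 and the planned analyses do not change.
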